### **3.17.1 Nursing Outcome Variables**

The data for nursing outcomes were collected in Phase II, historical control data were collected through a retrospective nurse audit of knowledge and skills in relation to KC management practices and assessing data on KC implementation techniques among mothers with premature infants. The nurses' perception, knowledge, and practice in relation to KC implementation were assessed using a set of structured questions, Questionnaire I for nurses, via a pre-test and then reassessed in a 7th day post-test following the program.

The researcher briefed the nurses and invited them, through a verbal briefing to the head nurse in charge of the selected unit, to participate in the study. On the same day as the pre-test, the Questionnaire I was given to the nurses, with two consent forms. Name, identification code number and date of attendance of the nurses who attended were recorded in order to plan the follow-up date for the post-test. The returned questionnaire was given an identification code number to ensure confidentiality and privacy. The consent form, including the questionnaire, was stamped in the right top corner with the code number, starting with nurse 01(N01). When nurses declined to continue the study, they were told to contact the researcher to ask for a withdrawal. Upon receiving an application for withdrawal from the study, the researcher destroyed the questionnaire, which was submitted based on the code number. All nurses were instructed to sit for the post-test on the 7th day after the pretest. The nurses were instructed to complete Questionnaire I for the pretest, which took about 15 to 20 minutes to complete, without referring to any resources before the KC-EP for nurses was conducted. Nurses were asked to return the questionnaires upon completion, together with one copy of the informed consent document. All nurses were expected to keep one copy of the informed consent form in their records. On the 7th day, the nurses were told to answer the same set of questions that had been used in the pretest. It was anticipated that an interval of 7 days would enable the posttest group nurses to translate their theoretical expertise into action and gain experience in evaluating, managing, and promoting the implementation of KC and also breastfeeding for mother-infant dyads through hands-on practice in the NICU environment.

### **3.18 Data Collection Procedures**

The ethical review was approved by the Medical Research Ethics Committee (MREC) with registered no: 201765-5310 before the study began. Formal permission was given by the management of UMMC, where the study was conducted, following a letter of request to

conduct research. Once permission was obtained, the unit managers were approached for permission to conduct the study in their respective units. The participants were assured their confidentiality and safety would be maintained and that there would be no exploitation of human rights or discrimination of any type based on the information given. After permission was granted, the researchers began selecting the participants (infant-mother dyads and nurses) based on the requirements of the inclusion and exclusion criteria. The researcher introduced herself and informed each of the participants about the nature of the study to ensure greater cooperation and to establish effective documentation throughout the data collection process. The researcher approached each participant individually and explained the study's purpose and how it would benefit them. Participants who showed a willingness to participate were selected as samples for this study. Each participant had a coding number assigned to ensure the anonymity and confidentiality of the information provided, and written informed consent was obtained. Two copies of the consent forms were given to both mothers with premature infants and nurses on the same recruitment day to obtain their consent to participate in the study. All participants were advised to keep in their records a copy of the informed consent form. The nurse participants were selected to be samples in this study using the universal sampling technique, which means the sample would represent the population of nurses in the NICU, while the infant-mother dyad participants were recruited based on infant-mother admission to the control group, or to the experimental group.

Firstly, the researcher collected a group of participants from the infant-mother dyads for the control group and made them comfortable. An orientation to the study was given before administering Questionnaire II, which required approximately 10 to 15 minutes to complete. All mothers were instructed not to interact or communicate while answering the questionnaire. On the same day, participants were asked to return the completed questionnaires to the researcher. An identification code number was provided for each

[figure not shown]
returned questionnaire to ensure confidentiality and privacy. The consent form and the questionnaire were stamped at the top right corner with the code number, for each set of questionnaires ( $T_0$ ,  $T_1$  and  $T_2$ ), starting with control group 01 (CG01) for the control group of mother-infant dyads. The pretest and posttest used the same structured Questionnaire II for baseline data from the mother-infant dyads in the control group. However, this group did not receive any special education program or any input related to KC from the researcher. All mothers were informed to answer the post-test questionnaire within the stipulated time of 1 month and 3 months after the discharge of their infant from the NICU. The collection of data from the control group of mothers was completed within six months, starting from early February 2018 to the end of July 2018.

Next, the researcher collected the group of participants from among the nurses, made them comfortable, and orientated them to the study. She then administered the structured quantitative-based Questionnaire II for nurses. All nurses were instructed not to interact with each other, and their doubts were clarified. The questionnaire took 10 to 15 minutes to complete; after completion the researcher asked the nurses to return the pre-test questionnaires as well as a copy of the informed consent form. All nurses were instructed to keep one copy of the informed consent form for their records. On the same day, nurses were asked to return the completed questionnaire to the researcher. Each questionnaire returned was given an identification code number to ensure confidentiality and privacy. For each set of questionnaires (pretest and post-test), the consent form and the questionnaire were labeled with a code number, beginning with N01 for the nurses, at the right top corner. The nurses' baseline data were gathered on demographic characteristics and KCQ tools (perception, knowledge and practice) regarding the KC technique. After the pre-test phase, the structured kangaroo care educational program (KC-EP) for nurses was conducted within two weeks for all  $n=47$  nurses. The program was delivered in English for the theory, and the practical

session included the showing of videos related to the KC transferring technique by the researcher. All nurses were informed to sit for the required post-test on the 7th day after the pretest phase and the KC-EP teaching module. The same structured Questionnaire I was administered at the post-test, and nurses were required to demonstrate the KC standing and sitting procedure. A checklist was provided for each nurse to assess her confidence and skills in relation to the KC technique. The collection of nurses' data lasted from 1st of August 2018 until the 30th of September 2018.

Finally, the researcher recruited a group of mothers with premature infants for the experimental group, returning to them in 48 hours. The researcher orientated the mothers to the nature of the study and administered Questionnaire I for the pretest, which required 10 to 15 minutes to complete. All mothers were instructed to not share or discuss anything with other group members and if discussion took place they were disqualified to continue the study. Once the questionnaires were completed they were collected by the researcher; the mothers required 10 to 15 minutes to complete Questionnaire I. The infant-mother participants' baseline data were gathered regarding demographic characteristics and KCQs tool (perception, knowledge, perceived barrier and stress level) for the pretest on KC technique. After the pretest, the mothers in the experimental group obtained information on KC in a group of two to four participants via the face to face teaching method; each group was accompanied by two of the nurses who were available in the NICU at that period of time. The KC-EP for mothers was conducted by the researcher and included a theory and practical session. The mothers were requested to answer the posttest at the 1st month and 3rd month of their premature infant's life after their discharge from the hospital. The same Questionnaire I was provided to the mothers for the posttest data. The collection of data from the mothers

was carried out within the stipulated time. After the data gathering process, the researchers thanked all the study participants as well as the authorities for their cooperation.

[figure not shown]

Figure 3.3: Flow Chart for Data Collection

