#### **1.4 Research Questions**

KC has gained acceptance as a chosen and effective technique for the quality care of premature infants. However, it is still a new phenomenon in the NICU in Malaysia; also no data has been published regarding the effectiveness of KC in relation to the perception, knowledge and, practices of nurses. In addition, emotional stress also occurs among those mothers whose preterm infants have been admitted to the NICU. This study also explores the outcomes of mothers in terms of their perception, knowledge, barriers and level of stress regarding KC implementation as well as the outcomes for their premature infants; weight gain, LOS and breastfeeding rates associated with compliance with the practice of KC in a Malaysian setting. In view of the lack of literature on a locally contextualized education model for the teaching of kangaroo care, I questioned the need for drafting such an education programme. The main research question of this thesis is;

Can a locally contextualised kangaroo care education programme aimed towards both mothers and NICU nurses be effectively implemented?

To answer the above research question, the following were analysed.

1. Are there any statistically significant changes in mothers' perception, knowledge, perceived barriers regarding KC and their level of stress after participation in a KC-EP between control and experimental groups of mothers at pre-intervention (T0), 1-month post-intervention (T1) and 3-months post-intervention (T2)?
2. Does KC improve premature infants' weight gain, LOS, and breastfeeding rates between a control and an experimental group at pre-intervention (T0), 1-month post-intervention (T1) and 3-months post-intervention (T2)?
3. Are there any statistically significant changes in the nurses' perception, knowledge and practice of KC before and after participation in a KC-EP?

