### **3.13 When, Where and How Much Will KC-EP be Delivered**

The question "When" refers to the timing, in particular the best time for the intervention program to be implemented and the question "How much" refers to the intervention's intensity in terms of the amount, duration and period of time needed to implement the intervention (Feeley, Nancy, Zelkowitz, Phyllis, Shrier, Ian, 2011). Timing and strength are two important aspects to be considered in the implementation of a nursing intervention. The duration and strength of the KC-EP implementation were agreed upon after analysis of literature review findings regarding mothers who were slightly more depressed at the beginning of enrolment. In the first week, the mothers were less stressed (Tandberg et al., 2013), and in the week after birth and the week after discharge, the mothers were most stressed and worried (Gennaro, York, & Brooten, 1990).

In this study, 48 hours after the admission of the premature infant to the NICU, or after the clinical stabilization of the infant, the expected intervention program was started, and the mother was able to perform KC. Within 48 hours post-admission, a specific orientation (reinforcement) and the first meeting were conducted. The second set of data was collected at the premature infant's age of 1 month (44 weeks). The duration and frequency of KC-EP

implementation were based on the guidelines (USIKC, 2018). Moreover, the Guidelines on Kangaroo Care, which was published by WHO (2003), was derived from Davanzo, Brovedani, Travani, Kennedy, Crocetta, Sanesi, Strajn., & De Cunto (2013). The duration or frequency of KC-EP implementation was also based on the Bakermans-Kranenburg, Van IJzendoorn, and Juffer (2003) studies. Meta-analysis results from Bakermans-Kranenburg et al. (2003) found that the most effective intervention consisted of less than 16 sessions, and that less than 5 sessions ( $d=0.33$ ) were as effective as a 5-16 session intervention ( $d=0.36$ ). Accordingly, after consideration of these findings by Bakermans-Kranenburg et al. (2003) the expert panel decided in this study to limit the number of sessions to the minimum possible in practice.

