### **3.14.5 Telephone call and short message via WhatsApp.**

To ensure continuity of the KC technique and quality of premature infant care, the researchers performed a follow-up through WhatsApp, sending a short message to the mother. This was a reminder about providing updates on the premature infant's performance of KC, the condition of the premature infant; i.e. body weight of preterm infant on discharge, at 1 month and 3 months corrected age, breastfeeding status every 2 weeks post-admission until 40 weeks post-admission. In addition, this continued every 4 weeks at 44 weeks, 48 weeks and 52 weeks of premature infant age [Table 3.2(a) & (b)]. The researchers also made three (3) telephone calls via WhatsApp during the program of which the first call was at 40 weeks post-admission, the second call was at 44 weeks (1 month) post-admission and the last call was at 52 weeks (3 months) post-admission. The purpose of the call was to find out if the mother had any doubts or had any problems linked to the objectives of the study at home and to advise the mother to contact the researcher at any time if she had any problems with KC and her premature infant's condition. All of the conversations were conducted using a very careful approach to ensure that the mothers were openly sharing their feelings and their appreciation of KC.

The program aimed to educate mothers on how to carry out KC and reduce their stress levels and how to strengthen their ability to breastfeed their premature infants. The nurses' workload in the NICU is generally very high, and nurses do not have enough time to assist

the mothers. Therefore, the entire program was allocated only 1 hour and 30 minutes. The experimental group had four sessions prepared and designed for the mothers, the specifics are set out in Appendix L and M. The program was administered in one session with between two (2) or four (4) mothers per group and one or two nurses involved at the first meeting. This was to ensure the nurses and mothers were given the same information , skills and shared attitudes.

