**Appendix L: Courses contents structured kangaroo care educational program (KC-EP) for mothers.**

 UNIVERSITY OF MALAYA	Course contents of Kangaroo Care Education Programme (KC-EP) for mother.
Educational Program Session (Participant)	All mothers in intervention group at neonatal intensive care unit (NICU) University Malaya Medical Centre (UMMC)
Course: Course Title: Medium of instruction Presenter :	Kangaroo Care Educationa Programme (KC-EP) Kangaroo Care Benefits for Premature Infant- Mother dyads and quality of care. Bahasa Malaysia and English [name]
Teaching materials/ Equipment	Laptop, LCD, white board, marker pen, lecture notes, showing video, pamphlets, booklet, infant dummy, baby sling, diapers, infant cap, all related forms applicable to the topic presentation and red & blue ball point.
Mode of teaching  Learning	Lecture-demonstration  Lecture (show and tell),practical (skill) & Question and Answer
Student learning time	Face to face (interpersonal communication): 1 hours Guide learning(theory):30 hours Assessment (practical) :30 hours
Presenter e-mail address	[name] [contact] @ [contact]
Theory & practical session: Day : Time : Venue :	Every Friday, Saturday and Sunday 10.00 am – 11.00 am. 12.00noon – 1.00pm or 3.00pm – 4.00pm & 5.00pm – 6.00pm Conference Room, Neonatal Intensive Care Unit, University Malaya Medical Centre, Klang Valley
General objective	At the end of the presentation the mothers will be able to have in depth understanding of kangaroo care in detail and demonstrate the procedure as well.
Specific objectives :	At the end of the presentation the mothers will be able to: 1) define term of kangaroo care (KC). 2) state the benefits of KC to infant-mother (breast feeding) 3) recognize sign and symptoms of deterioration among premature infant before, during and after the procedure 4) state the preparation before, during and after the KC procedure. 5) list the equipment for KC procedure; 5.1 infant 5.2 mother 6) demonstrate and return-demonstrate & charting the infant progress record by the nurses to mothers
Important dates (Primary and Secondary outcomes)	Pretest & posttest after 1 st month and 3 rd months of KC-EP for mothers.

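### T1 and T2 for the mothers' questionnaires are timed from the intervention, from infant age and from NICU discharge in different sections, and Section 3.18 words the two arms differently

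*Combined protocol and SAP*

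**What the plan says.** The mothers' outcomes (perception, knowledge, perceived barriers, stress) are measured three times and compared between arms with a general linear model and repeated measures (Section 3.19.1, Table 3.4). The timing of the second and third measurement is given in several ways:

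- **From the intervention.** Section 1.4 defines T1 as "1-month post-intervention", with T2 at three months on the same origin. Appendix L places the post-tests after the first and third "months of KC-EP for mothers".
- **From infant age.** Section 3.13: "The second set of data was collected at the premature infant's age of 1 month (44 weeks"). Table 3.2(b) lists the questionnaire at infant weeks 44 and 52, for both arms.
- **From discharge, control arm.** Section 3.18 has control mothers answer "1 month and 3 months after the discharge of their infant from the NICU".
- **Mixed, experimental arm.** A later paragraph of Section 3.18 gives the first and third month of the infant's life, following discharge. This can be read as age or as time since discharge.
- **No origin.** Section 3.16.1 hands control mothers the questionnaires at clinic follow-up in the first and third month, without saying counted from what.

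For infant weight, Section 3.14.5 is explicit: "body weight of preterm infant on discharge, at 1 month and 3 months corrected age". The documentation slide in Appendix P agrees. However, Section 3.16.4 computes weight gain from discharge, T1 and T2 weights under the same labels, and its subsection on infant outcomes runs data collection to three months of age after discharge.

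No section says which definition governs, and no visit window is given.

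**The concern.** A group-by-time analysis assumes that T1 and T2 mean the same thing in both arms. Here they may not, for two reasons.

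First, Section 3.18 gives the two arms different wording. If each paragraph was followed as written, control mothers may have been assessed on a discharge clock and experimental mothers on an age clock.

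Second, discharge is not a neutral origin even if both arms use it. Length of stay is a primary outcome (Section 3.9) and H2 expects KC to improve it (Section 1.6). Counting from discharge lets a hypothesised effect of the intervention set the infant's age when the mother is questioned. The intervention clock has a different defect: it has no meaning for controls.

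At stake is whether a difference in stress, knowledge or barrier scores reflects the programme or a difference in when the mothers were asked. The stress scale is about separation and not being able to care for the infant, so time since discharge plausibly matters to the answers.

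**Working it through.** The plan gives no figure for visit timing to reproduce. Its one design calculation is unaffected: 2 × (1.96 + 0.842)² × 0.64 / 0.54² = 34.46, so 35 per group, and 35 / 0.70 = 50.

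**Do the clocks agree?** Ages are on the scale where 44 weeks is one month corrected. One calendar month is 30.44 days, or 4.35 weeks; three months are 13.04 weeks.

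*Age clock (Table 3.2).* T1 = 44 and T2 = 52 weeks in both arms.

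*Intervention clock.* Recruitment is at 28 to 36+6 weeks (Section 3.7.1). Taking the programme to start at recruitment (assumption):
- T1 = 28 + 4.35 to 36.86 + 4.35 = 32.3 to 41.2 weeks, which is 11.7 to 2.8 weeks before week 44.
- T2 = 28 + 13.04 to 36.86 + 13.04 = 41.0 to 49.9 weeks, which is 11.0 to 2.1 weeks before week 52.

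*Discharge clock.* Age at discharge is not given, so 34 to 40 weeks is assumed.

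| Discharge (weeks) | T1 (weeks) | Days before 44 | T2 (weeks) | Days before 52 |
|---|---|---|---|---|
| 34 | 38.3 | 40 | 47.0 | 35 |
| 36 | 40.3 | 26 | 49.0 | 21 |
| 38 | 42.3 | 12 | 51.0 | 7 |
| 40 | 44.3 | −2 | 53.0 | −7 |

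The discharge and age clocks coincide only when discharge falls at 44 − 4.35 = 39.7 weeks (T1) or 52 − 13.04 = 39.0 weeks (T2). Discharge depends on a predetermined weight, weight gain and sucking (Section 3.16.4), not on reaching that age. The wordings are therefore not interchangeable.

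**How far apart could the arms be if both used the discharge clock?** The shift in infant age equals the difference in length of stay. The length-of-stay review in Chapter 2 cites:
- 17.68 − 11.46 = 6.22 days
- 20.7 − 16.6 = 4.1 days
- 12.86 − 12.78 = 0.08 days

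The range is about 0 to 6.2 days.

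**Weight, only if attained weight were taken on that clock.** At 15 to 20 g/day (discharge rule in Section 3.16.4; follow-up slide in Appendix P):
- 6.22 × 15 = 93 g and 6.22 × 20 = 124 g
- 4.1 × 15 = 62 g and 4.1 × 20 = 82 g
- 0.08 × 15 = 1.2 g and 0.08 × 20 = 1.6 g

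The standard deviation of attained weight is not given. For an assumed 500 to 900 g, the largest figure is 124/900 = 0.14 to 124/500 = 0.25 SD. The standardised effect in the sample-size formula is 0.54/0.8 = 0.675.

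**Questionnaires.** No corresponding figure can be computed, because the documents give no rate at which scores change with time.

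**The case against.** The best defence is that Table 3.2 is the formal schedule, lists both arms side by side, and puts the questionnaire at weeks 44 and 52 in each. On that view the other wordings are loose descriptions of the same visits. This shows that unequal timing is possible rather than certain. It does not settle the matter, because nothing says the table governs and Section 3.18 is the procedure that describes what mothers in each arm were told.

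Three stronger readings are tempting and are not supported.

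- **That the primary weight outcome is biased.** The discharge clock is attached to the questionnaires. Where a clock is stated for weight, it is corrected age. Weight is also recorded as grams per day, and gain over a fixed interval from discharge covers the same span in both arms; neither picks up the gram shift above. What remains is the reuse of the T1/T2 labels in Section 3.16.4, so the single definition should cover weight as well.
- **That admission is a fourth clock.** Section 3.14.5 says "the second call was at 44 weeks (1 month) post-admission", but this describes telephone support listed only under the experimental arm's activities in Table 3.2, not T1/T2 data. Read literally, 44 weeks cannot be one month after admission.
- **That the gap of several weeks between clocks is a between-arm bias in weight.** The table above shows how far two definitions differ for one infant. It becomes a difference between arms only if the arms used different clocks, and then for the data collected on them.

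It is also fair to say that 6.2 days is the most favourable contrast cited. It comes from infants under 1.5 kg, a narrower group than this trial's, and the same review cites a randomised trial with practically no difference.

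**Conclusion.** The timing of T1 and T2 is inconsistent for the mothers' questionnaires and should be corrected. The intervention, infant-age and discharge origins are all explicit, they give materially different dates for most plausible discharge ages, and Section 3.18 words the arms differently. A discharge origin is unsafe because H2 expects the intervention to move it.

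The documents show that the arms can have been measured at different times, not that they were. If both arms followed discharge, the shift in infant age is about 0 to 6.2 days, depending on which cited length-of-stay contrast applies. If the arms followed different clocks, it could run to weeks under the assumed discharge ages.

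For weight, about 0 to 124 g applies only if attained weight was analysed on the discharge clock. Its direction is uncertain: earlier discharge makes an infant younger at assessment, but an infant discharged earlier may also have reached the required weight sooner. The sample size is unaffected.

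**What to change.** Define T1 and T2 once, for all mother and infant data in both arms, as 44 and 52 weeks corrected age, following Table 3.2. Add a common window, for example plus or minus one week. Bring Section 1.4, the infant-outcome subsection of Section 3.16.4, both mothers' paragraphs of Section 3.18 and Appendix L into line with that definition.

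Record the infant's actual age at each assessment and report its distribution by arm. Sections 3.7.2 and 3.16 describe recruitment and data collection as complete by April 2019, so for those data derive age from recorded dates and state which clock was in fact used in each arm.

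Use adjustment for age at assessment only as a sensitivity analysis. If visits followed discharge, that age is itself affected by the intervention, and conditioning on it in the main model would bring back the problem.

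The cost is rewording, extraction of dates and one additional analysis. Clinical care and sample size do not change.
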